**PROTOCOL SUMMARY**

Sponsor	The University of Washington
Protocol Title	Branched Thoracic Endovascular Grafts for the Treatment of Thoraco-abdominal Aortic Aneurysms (B-TEVAR)
Study Description	
An investigator-initiated, prospective, consecutively enrolling, non-randomized single institution clinical evaluation of the safety and effectiveness of either: 1) physician modification of a currently FDA- approved off the shelf thoracic aortic stent graft (COOK Zenith® TX2®); or
 
2) Thoracoabdominal Custom Branch/Fenestrated Endovascular Stent-Graft (Cook Medical); or 3) Cook t-Branch Endovascular Stent Graft or 4) Cook Low Profile (LP) t-Branch or Custom Made Device (CMD) to preserve branch vessels when used in the treatment of patients with thoraco-abdominal aortic aneurysms.

Study Objectives	
The primary objectives of this study are to determine whether physician modified branched endovascular grafts are a safe and effective method of treating patients with thoraco-abdominal aortic aneurysms.
 
The safety of physician modified endovascular grafts will be determined by evaluating the proportion of patients that experience a rate of Major Adverse Events.
 
The effectiveness of physician modified endovascular grafts will be determined by evaluating the proportion of patients that achieve Treatment Success at 12 months post-procedure.

Study Primary Endpoints	
The primary safety endpoint is defined as the proportion of subjects who experience a Major Adverse Event within 30 days of the B-TEVAR procedure.
 
The primary effectiveness endpoint is the proportion of subjects that achieve Treatment Success. Treatment Success is a composite endpoint assessed at 12 months following implantation of the B-TEVAR device that requires the following criteria to be met:
 
 
• Technical Success, defined as successful delivery and deployment of the physician modified graft with preservation of unimpeded flow to those branch vessels intended to be preserved.
 
• Freedom from Type I & III endoleaks
 
• Freedom from stent graft migration
 
• Freedom from aortic aneurysm enlargement
 
• Freedom from aortic aneurysm rupture
 
• Freedom from conversion to open repair
 

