#### **7.1 Primary Objectives**

The primary objective of this study is to determine if branched endovascular grafts are a safe and effective method of treating TAAAs. Treatment success is defined as successful deployment of the modified endograft and its branches with preservation of unimpeded flow to all target vessels that are intended to be preserved. Failure to exclude the aneurysm (i.e. Type 1 or 3 endoleak), conversion to an open operation, aneurysm rupture, thrombo-embolic complication to a target

vessel, kink/stenosis of a branch stent or flow limiting distal branch vessel dissection will be considered treatment failure. Any such branch related events that are identified intra-operatively and successfully treated will not be considered treatment failures.

The safety of the endovascular grafts will be determined by the proportion of patients with major adverse events. The effectiveness of the endovascular grafts will be determined by the proportion of patients that achieve treatment success.

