### 8.5 TAAA Enlargement

Aneurysm enlargement is defined as a greater than 5 mm (diameter) increase in the orthogonal plane of the aneurysm size. Spiral CT images will be used to determine aneurysm enlargement at regularly scheduled follow-up visits. The 1 month image will be used as the baseline for subsequent assessment.

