### **8.14 Technical Failures**

In the event that a branched stent graft could not be deployed due to a technical failure, device failure information will be captured on the **Device Failure CRF**.

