### **8.15 Deaths**

Any deaths that are device related must be reported to the FDA via an IDE supplement within 10 business days of knowledge of the event. Any deaths that are not device related are reported annually. The investigator is also required to adhere to the reviewing IRB requirements for reporting of deaths. In addition, patients with an implanted device who expire before completing the study should have the device explanted for evaluation by a pathologist if possible.

Aneurysm related death is defined as:

- any death occurring within 30 days of the B-TEVAR procedure, regardless of cause,
- death due to aneurysm rupture or
- within 30 days following any secondary procedure intended to treat the aneurysm.

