### 9.1 Primary Endpoints

#### 9.1.1 Safety

The primary safety endpoint is the rate of major adverse events (MAE) at 30 days post branched TEVAR repair. The following specific events will be considered major adverse events: MAEs are defined as any one of the following events:

- Death
- Paralysis (excludes paraparesis)
- Myocardial Infarction
- Stroke (excludes TIA)
- Renal Failure (excludes renal insufficiency)
- Respiratory Failure (excludes COPD or pulmonary complications)
- Bowel Ischemia
- Lower Extremity Ischemia
- Procedural Blood Loss ( $\geq 1,000$  cc)

MAEs may or may not be considered related to the device. Mortality will be reported as “all cause” and “TAAA related.” All deaths occurring in the first 30 days post-index procedure are considered “TAAA related.”

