#### 9.1.2 Effectiveness

The primary effectiveness endpoint is the proportion of treatment group subjects that achieve treatment success with the B- TEVAR procedure, whether via the staged approach or done as a single procedure . Treatment success is a composite endpoint assessed at 12 months after the B-TEVAR procedure is performed that requires all of the following criteria to be met in order for a patient to be considered a treatment success:

- Technical Success, defined as successful delivery and deployment of the endovascular graft with preservation of unimpeded flow to those branch vessels intended to be preserved.
- Freedom from Type I & III endoleak. Type I and III endoleaks will be assessed by the investigator using Spiral CT images.
- Freedom from stent graft migration. Migration of the aortic stent graft is defined as evidence of proximal or distal movement of the stent graft >10 mm relative to fixed anatomic landmarks. Migration of a branch is defined as movement of the stent in relation to fixed anatomic location that results in a Type I or III endoleak. Spiral CT images will be used by the investigator to determine migration from the one month (baseline) CT image.
- Freedom from TAAA enlargement. Sac enlargement is an increase in aneurysm diameter (>5 mm) from the one month (baseline) post-operative measurement will be considered TAAA enlargement, as determined by the investigator.
- Freedom from TAAA rupture
- Freedom from conversion to open repair

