## 9.2 Secondary Endpoints

### 9.2.1 Safety

The following secondary safety endpoints will be evaluated at 30 days, 12 months and annually to 5 years:

- All-cause mortality
- TAAA Related Mortality
- Freedom from permanent spinal cord injury
- Major Adverse Events (MAE)
- TAAA rupture
- Surgical conversion

The CEC will meet annually to review all MAE. All deaths that occur in the study will be adjudicated by the CEC. TAAA related death is any death determined by the CEC to occur as a result of the initial procedure (first 30 days or prior to hospital discharge), TAAA rupture, conversion to open surgical repair, or due to secondary intervention after B-TEVAR.

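### Does the Treatment Success composite need a survival item, or a written rule for patients who die before the 12-month assessment?

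*Protocol*

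**What the plan says.** Section 9.1.2 takes as its endpoint the proportion of Treatment Group subjects who reach Treatment Success. It is "assessed at 12 months after the B-TEVAR procedure is performed that requires all of the following criteria to be met", and the six criteria follow. The Protocol Summary repeats the same six: "Treatment Success is a composite endpoint assessed at 12 months following implantation of the B-TEVAR device that requires the following criteria to be met". Endoleak, migration and enlargement are judged on CT. For enlargement, section 8.5 adds "The 1 month image will be used as the baseline for subsequent assessment", and section 8.2 does the same for aortic migration.

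Section 7.1 gives a looser account without a time point. Its failures begin "Failure to exclude the aneurysm (i.e. Type 1 or 3 endoleak), conversion to an open operation, aneurysm rupture" and continue with branch events. Death is not in the list.

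Death is handled under safety. It is the first item of the 30-day major adverse event composite in section 9.1.1, which adds "All deaths occurring in the first 30 days post-index procedure are considered" TAAA related. Section 9.2.1 lists all-cause and TAAA-related mortality at 30 days, 12 months and annually to 5 years, with every death adjudicated by the Clinical Events Committee.

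Section 6.5 analyses everyone who received the B-TEVAR device as one group and puts staged patients who never reach the second stage in a separate analysis. The Secondary Effectiveness section (numbered 1.2.2) reuses Treatment Success at 30 days and annually.

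**The concern.** Deaths within 12 months are to be expected: enrolment requires high risk for open repair and ASA class 3 or above. Read item by item, a patient who died event-free after a clean 1- or 6-month CT could be said to have met each freedom-from criterion. Alternatively, a patient with no 12-month CT could be dropped as not assessable. Either choice raises the success proportion relative to counting the death as a non-success. The same data could then yield different primary effectiveness figures, with the choice made after the deaths are known.

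It also looks odd that a death the protocol itself calls TAAA related need not be a listed effectiveness failure. Rupture and conversion deaths already fail through their own criteria. Other deaths within 30 days or before discharge, and deaths after a secondary intervention without conversion, do not.

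**Working it through.** **What the text supports**

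- *Non-success.* Success must be established at 12 months, every criterion must be met, and the denominator is the Treatment Group. A patient who has died cannot have the 12-month CT assessment, so success is not shown and the patient stays in the denominator.
- *Last status.* No section carries a 1- or 6-month scan forward to month 12. After a death before the 1-month CT, migration and enlargement do not even have a baseline.
- *Exclusion.* No section defines an evaluable subset. Section 6.5 keeps all implanted patients together. Technical Success is itself a criterion, so failed deployments belong in the denominator; section 8.14 ("In the event that a branched stent graft could not be deployed due to a technical failure") only assigns them a form.
- *Section 7.1.* Its failure list also omits migration and enlargement, which 9.1.2 includes. It is therefore not exhaustive, and its silence on death says little.
- *30-day reuse.* At 30 days migration and enlargement are uninformative for living patients too, because the 1-month image is the baseline. The Summary lists the separate components at that visit, not the composite.

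**Size**

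The protocol states no target or expected success rate, so there is no figure of its own to reproduce.

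Inputs:
- n = 60 (section 5.0).
- Mortality in two series cited in section 2.1.4: 18.5% at 1 year and 6.3% at 30 days; 13% at 1 year (87% survival) and 9% at 30 days.
- Success among survivors s = 0.7 to 0.9. This is assumed.
- Share of deaths free of a listed failure: one half, or all as an upper bound. This is also assumed.

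Expected 12-month deaths: 60 × 0.13 = 7.8, taken as d = 8; 60 × 0.185 = 11.1, taken as d = 11.

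| Quantity | Formula | d = 8 | d = 11 |
|---|---|---|---|
| Death = non-success | s(60 − d)/60 | 60.7 to 78.0% | 57.2 to 73.5% |
| Rise if half the deaths are excluded | s(60 − d)/(60 − d/2) − s(60 − d)/60 | 4.3 to 5.6 points | 5.8 to 7.4 points |
| Rise if half are scored as successes | (d/2)/60 | 6.7 points | 9.2 points |
| Rise if all are excluded | s·d/60 | 9.3 to 12.0 points | 12.8 to 16.5 points |
| Rise if all are scored as successes | d/60 | 13.3 points | 18.3 points |

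The last-status reading needs a 1-month scan, so only later deaths qualify. These are about 18.5 − 6.3 = 12.2% and 13 − 9 = 4.0% of patients. If half are event-free, the rise is 6.1 and 2.0 points.

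At 30 days, 60 × 0.063 = 3.8 and 60 × 0.09 = 5.4, taken as 4 and 5 deaths. With half event-free the rise is 2.3 to 3.6 points if excluded and 3.3 to 4.2 if scored as successes. The upper bound is 5/60 = 8.3.

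Sampling half-width: 1.96 × √(p(1 − p)/60) is 10.5 points at p = 78.0% and 12.5 at p = 57.2%.

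The 60 include staged patients who may never receive B-TEVAR, so death counts in the implanted group would be lower.

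**The case for a change.** The strongest case for a change is that the components of a primary composite are fixed in the protocol, not in an analysis plan. Death is a foreseeable outcome here, not a missing scan. Both alternative scorings move the figure upward, so the shift is systematic and is not excused by being smaller than the sampling error. One sentence would close the question.

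Part of this stands. No sentence states the rule, and an explicit one would do no harm. But that sentence would only write down what 9.1.2 already yields when read as a whole. The detailed handling of patients without an assessment, including living patients lost to follow-up or without a 12-month CT, commonly sits in a statistical analysis plan. One may exist here but was not available.

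Going further would be a matter of preference. Counting all deaths as effectiveness failures brings co-morbid deaths into a device measure. Counting only aneurysm-related deaths requires choosing between two definitions: section 8.15 includes "any death occurring within 30 days of the B-TEVAR procedure, regardless of cause", while section 9.2.1 says "TAAA related death is any death determined by the CEC to occur as a result of the initial procedure" and extends the window to hospital discharge.

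The distance between those two choices can be estimated. Take only the cited 30-day deaths as TAAA related and let later event-free deaths, a fraction o of patients, leave the denominator. With 1-year mortality m, the TAAA-only proportion exceeds the all-cause one by s(1 − m)/(1 − o) − s(1 − m). With m = 0.13 and o = 0.04 this is 2.5 to 3.3 points; with m = 0.185 and o = 0.122 it is 7.9 to 10.2. Halving o gives 1.2 to 1.6 and 3.7 to 4.8. Either choice is defensible, and reporting mortality separately serves the same purpose.

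**Conclusion.** No change to the plan is called for. The composite has no survival item, but its wording makes a patient who dies before 12 months a non-success, and neither alternative scoring has support in the protocol. What is left is an unwritten rule that an analyst would fill in the conservative direction. Whether all-cause or TAAA-related death should count as an effectiveness failure is a fair trade-off.

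If an analyst did depart from that reading, the proportion would rise by 4.3 to 9.2 points with half the deaths event-free and by at most 18.3 with all of them so. These figures rest on mortality in two cited series, an assumed 70-90% success among survivors and an assumed share of event-free deaths. The largest upper bounds exceed the sampling half-width; the half-of-deaths figures do not. With no test or performance goal, and with deaths reported under primary and secondary safety, a reader can see the deaths beside the success proportion, and no conclusion turns on the scoring.

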## 9.2 Secondary Endpoints

### 9.2.1 Safety

The following secondary safety endpoints will be evaluated at 30 days, 12 months and annually to 5 years:

- All-cause mortality
- TAAA Related Mortality
- Freedom from permanent spinal cord injury
- Major Adverse Events (MAE)
- TAAA rupture
- Surgical conversion

The CEC will meet annually to review all MAE. All deaths that occur in the study will be adjudicated by the CEC. TAAA related death is any death determined by the CEC to occur as a result of the initial procedure (first 30 days or prior to hospital discharge), TAAA rupture, conversion to open surgical repair, or due to secondary intervention after B-TEVAR.

### 1.2.2 Secondary Effectiveness

The following secondary effectiveness endpoints will be evaluated at 30 days, 12 months and annually to 5 years:

- Need for re-intervention

- Treatment success as defined in section 9.1.2

### **9.3 Clinical Utility Measurements**

The following Clinical Utility measurements associated with both the B-TEVAR and the TEVAR alone will also be assessed:

- Conduit use
- Amount of blood loss
- Days spent in ICU
- Days spent in hospital
- Type of Anesthesia
- Placement of lumbar drain
- Rationale for planned staged approach and for any patient who is unable to undergo a second stage
- Discharge status to home, nursing facility, and assessment of functional status

## **10.0 RISKS AND RISK ANALYSIS**

Treatment of a thoraco-abdominal aneurysm with both endovascular and open surgical repair poses significant inherent risks to the patient. The mortality risk of open surgical repair of a TAAA is greater for those patients with risk factors, such as advanced age and medical comorbidities (i.e. cardiac, renal and pulmonary).

Endovascular treatment of a TAAA has been shown to be an effective, less invasive procedure that may result in reduced early mortality and morbidity, reduced need for blood products, shorter hospital stays and recovery time, as well as improved quality of life in the early postoperative period.

In order for patients to participate in the Treatment Group of this study, they must agree to adhere to a strict follow-up schedule to continuously monitor their long term safety.

Our understanding of the risks associated with the use of branched and fenestrated-branched aortic endografts are outlined in Section 2.1.4. Although the adverse events associated with the use of endovascular grafts may be less than for standard open surgical repair, inherent risks exist, as with many medical procedures. However, risks that have been associated with repair of TAAAs with this type of device include, but may not be limited to:

- Cardiac events such as congestive heart failure (CHF), volume overload, arrhythmias, myocardial infarction (MI), chest discomfort or angina, elevations in creatinine phosphokinase (CPK), hypotension, hypertension

- Pulmonary events such as pulmonary insufficiency, pneumonia, respiratory depression or failure, pulmonary edema, pulmonary embolism
- Cerebral events such as cerebrovascular accident (hemorrhagic or embolic), reversible ischemic neurologic deficit, transient ischemic attacks (TIA)
- Acute and chronic renal insufficiency or failure, need for dialysis, renal artery stent occlusion or renal embolization, need for re-intervention
- Operative and post-operative bleeding disorders, hemorrhage and coagulopathy
- Insertion and other vascular access site complications such as infection, bleeding, delayed healing, hematoma, dehiscence, seroma, nerve injury/damage, neuropathy, neuralgia, vasovagal response
- Vascular injury including damage to blood vessels and surrounding tissues, vessel dissection, perforation, plaque dissection, collateral vessel occlusion, tissue loss, arterial fistula, limb loss, gangrenous disease, worsened or new onset claudication, edema
- Neurological complications, such as paralysis (temporary or permanent), paraplegia, monoplegia, paresis, spinal cord ischemia, hemiplegia, bowel or bladder incontinence
- Multi-system organ failure
- Embolic and thrombotic events such as deep vein thrombosis, thromboembolism, microembolism, thrombophlebitis, pulmonary embolism, air embolism
- Gastrointestinal events such as paralytic or adynamic ileus, obstruction, fistulas, and Intestinal ischemia due to visceral artery injury, branch failure, or embolization
- Impotence, erectile dysfunction
- Urinary events such as hematuria, urinary retention, and urinary tract infection
- Radiation injury, late malignancy
- Allergic reaction to x-ray dye such as flushing, nausea, vomiting, itching, hives
- Generalized inflammatory response that may be associated with elevated levels of systemic mediators of inflammation, elevated temperature
- General discomfort related to the procedure or tests, sore throat, pain
- Infection— systemic or localized, sepsis, endograft
- Device events such as endograft occlusion, migration, dislodgement, endoleak, failure to align the fenestrations with the visceral arteries and/or stent fracture
- Irreversible (permanent) tissue loss (for example loss of fingers, toes hands and/or feet)
- Potential whole body reaction (SIRS - Systemic Inflammatory Response) to the grafts that are placed causing an acute inflammatory (protective tissue response to injury or destruction of tissues) response that is seen by an increased heart rate, increased breathing rate, a white blood count that is either increased or decreased, increased or decreased body temperature. These conditions may lead to organ failure such as kidney failure potentially requiring the need for dialysis, respiratory failure potentially requiring the need to be on a ventilator (breathing machine), anemia potentially requiring the need for transfusions

- Branch vessel occlusion
- Aneurysm rupture
- Conversion to open surgical repair
- Death

The subset of patients who undergo a planned staged procedure will be at risk of interval rupture and death between the initial TEVAR procedure and the second B-TEVAR procedure. The specific risk is unknown as there are no data to inform this risk estimate.

Patients who do not tolerate the TEVAR procedure and therefore do not go on to the second completion stage will remain at risk of death from aneurysm rupture.

Potential benefits of endovascular grafts compared to open surgical aneurysm repair may include, but are not limited to:

- Freedom from open surgery;
- Reduction of complications;
- Freedom from general anesthesia and/or the ability to use other forms of anesthesia that do not require mechanical ventilation; and
- Reduction in hospitalization and recovery time.

## **11.0 STUDY RESPONSIBILITIES**

### **11.1 Responsibilities of Investigator**

The investigator is responsible for properly conducting the investigation, ensuring that proper monitoring, IRB review and approval are obtained, submitting the IDE application to the FDA and ensuring that reviewing IRBs and the FDA are promptly informed of significant new information about the study.

The FDA retains the right to terminate the study at any time. Specific instances, which may precipitate study termination, are:

- Unsatisfactory patient enrollment with regard to quality and quantity.
- Deviations from protocol, without prior approval from the FDA.
- Inaccurate, incomplete, and/or untimely data recording on a recurrent basis.
- The incidence and/or severity of adverse experiences in this or other studies indicating a potential health hazard caused by the device.

### **11.2 FDA and IRB approval**

The investigator will not begin an investigation until an IRB and the FDA have both approved the IDE.

### **11.3 Data Safety Monitoring Plan**

The investigator will develop and maintain a DSMP to be managed by monitor(s) qualified by training and experience to monitor the study in accordance with applicable FDA regulations.

### **11.4 Accountability and Control of Devices**

The investigator shall maintain adequate records of the disposition of all investigational devices. As this device is currently commercially available and approved by the FDA, device lot numbers will be recorded.

